Secondary outcomes, will use ANOVA or Kruskal-Wallis test to analyze cost effectiveness. depending if data is normally distributed for comparison of the three treatment arms. If significant, we will further analyze with pair-wise comparisons by using t-test or Wilcoxon rank-sum test with the Bonferroni correction to control for type I experiment-wise error rate of 0.05.

Rates of healing among the four groups will be analyzed using log-rank test to compare time of healing within 20 weeks.

Descriptive statistics will include demographics, smoking history, and characteristics of the wound. For comparison nominal categorical secondary outcome variables, we will use Chi-square test. For comparison of ordinal categorical variables, we will use the Wilcoxon rank-sum test (for two independent group comparison) and Kruskal-Wallis test (for three independent group comparison).

TABLE OF CONTENTS

- 1 BACKGROUND AND RATIONALE
- 2 OBJECTIVES
- 3 STUDY POPULATION
- 4 STUDY PROCEDURES
 - 4.1 DESIGN AND METHODOLOGY
 - 4.2 DESCRIPTION OF STUDY GROUPS
 - 4.3 STUDY FLOW CHART
 - 4.3.1 SCREENING/BASELINE PERIOD (VISIT 1 to 2/WEEKS -1 to -2)
 - 4.3.2 RANDOMIZATION (VISIT 3/WEEK 0)
 - 4.3.3 TREATMENT PHASE (VISIT 4/WEEK 1)
TREATMENT PHASE (VISIT 5/WEEK 2)
TREATMENT PHASE (VISIT 6/WEEK 3)
TREATMENT PHASE (VISIT 7/WEEK 4)
TREATMENT PHASE (VISIT 8/WEEK 5)
TREATMENT PHASE (VISIT 9/WEEK 6)
TREATMENT PHASE (VISIT 10/WEEK 7)
TREATMENT PHASE (VISIT 11/WEEK 8)
TREATMENT PHASE (VISIT 12/WEEK 9)
TREATMENT PHASE (VISIT 13/WEEK 10)
TREATMENT PHASE (VISIT 14/WEEK 11)
TREATMENT PHASE (VISIT 15/WEEK 12)
TREATMENT PHASE (VISIT 16/WEEK 13)
TREATMENT PHASE (VISIT 17/WEEK 14)
TREATMENT PHASE (VISIT 18/WEEK 15)
 - 4.3.4 STUDY ENDPOINT (VISIT 19/WEEK 16)
 - 4.3.5 FOLLOW-UP PHASE (VISIT 20/WEEK 17)
FOLLOW-UP PHASE (VISIT 21/WEEK 20)
FOLLOW-UP PHASE (VISIT 22/WEEK 24)
FOLLOW-UP PHASE (VISIT 23/WEEK 28)
- 5 ADVERSE EVENTS
- 6 STATISTICAL DESIGN
- 7 REFERENCES
- 8 APPENDIX

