2 OBJECTIVES

The primary objective of this study is to assess the effectiveness of cellular dermal replacement tissue vs. non-viable extracellular matrix (ECM) for the treatment of non-healing diabetic foot ulcers. The primary endpoint will be the measurement of wound closure at 12 weeks, secondary outcomes will be measured at 20 weeks and the rate of healing in each treatment arm.

The secondary objective of study is to determine cost effectiveness of the bioengineered cellular vs. acellular ECM products. Cellular ECMs (Dermagraft®) are costly devices, \$1800 per application, difficult to use and time sensitive (weeks). The acellular ECM (Oasis®) is easier to use and at a cost \$80 per application and has a longer shelf life (2 years). These devices typically require multiple applications, on a weekly basis. If the findings show that these devices are equivalent, then the use of acellular ECM would lead to significant savings for the VA. Genetic markers of non-healing vs. healing diabetic ulcers will also be investigated, which will be useful information in predicting healing potential.

[figure not shown]

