4.2 DESCRIPTION OF STUDY GROUPS

Standard (Conventional) Therapy:

Standard therapy will consist of the typical foot evaluation and care provided by the Department of Veteran Affairs facilities, which will include weekly sharp debridement, cleansing of wound with normal saline, and application of non-adhesive dressing (Adaptic® or Mepitel®), Iodosorb® gel over wound bed, covered by dry dressings. The investigator will document the standard care provided during clinic visits including weekly follow-up evaluations. Offloading will be standardized, which will involve placement in modified offloading insert (trilaminar plastazote) and removable Cam Walker boot.

Oasis®:

Patients in the Oasis® group will undergo the same wound care and offloading modality as the Standard Therapy group, with weekly wound evaluation dressing changes. The Oasis® matrix will be applied on the wound (cut to size), moistened with normal saline to assure adherence to wound bed, then apply non-adhesive dressing (Adaptic® or Mepitel®), moist sterile gauze, dry and gauze dressings. Up to 8 weekly applications will be applied to wound until healed.

Dermagraft®:

Patients in the Dermagraft® group will receive the same Standard Therapy, with weekly wound evaluation and dressing changes. The Dermagraft® will be thawed as directed by the manufacturer, then under sterile technique Dermagraft® will be cut to size of wound, covered with non-adhesive coverage (Adaptic® or Mepitel®), moistened sterile gauze and dry dressings. Up to 8 weekly applications will be applied to wound until healed.

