We will perform a cost-effectiveness analysis comparing the treatment groups Dermagraft®, Oasis® and the standard care group at the NCHCS using ANOVA or Kruskal-Wallis test depending if data is normally distributed for comparison of the three treatment arms. If significant, we will further analyze with pair-wise comparisons by using t-test or Wilcoxon rank-sum test with the Bonferroni correction to control for type I experiment-wise error rate of 0.05. A p-value less than $0.05/3 = 0.0167$ will be considered statistically significant.

We will evaluate the cost-effectiveness of the Oasis® compared to Dermagraft® and the standard of care by measuring QALYs as the measure of effectiveness, based on results obtained from SF-36v2™ questionnaire. Multiple regression will be used to allow to evaluate continuous dependent variable outcomes, including change scores between baseline and end of study physical (PCS) and mental (MCS) component summaries from the SF-36v2™ questionnaire.

Rates of healing among the three groups will be analyzed using log-rank test to compare time of healing within 20 weeks among the 3 treatment groups.

Secondary endpoint (complete healing at 20 weeks), recurrence ulceration rate at 20 weeks will be analyzed using Chi-square tests. In addition, demographics, smoking history, and characteristics of the wound will also be summarized in table. Data that are continuous variables will be summarized by using mean, median, standard deviation, coefficient of variation, minimum and maximal values. Frequency tables will summarize categorical variables.

Timeline and Milestones:

Months	Year 1		Year 2	
	1-6	7-12	1-6	7-12
Aim 1: Recruitment				
Step 1: Screening (2-week run-in phase)	✓	✓	✓	
Step 2: Randomization/Assignment	✓	✓	✓	
Aim 2: Data Collection				
Step 1: Healed by Week 12	✓	✓	✓	✓
Step 2: Wound not healed by Week 12, continue in study until Week 20	✓	✓	✓	✓
Step 3: If wound has not reached closure beyond the 8 weeks of Dermagraft® – will switch to standard of care (expensive). Oasis® – continue to the end of study	✓	✓	✓	✓
Aim 3: Data Analysis				
Step 1: Outcome effectiveness If outcome show significant difference will cross over for intent-to-treat	✓	✓	✓	✓

7 References

1. Vista/CPRS data record system from 2006-2008, retrieved on 4/7/2009.
2. Vista/CPRS data record system from 2006-2008, retrieved on 4/7/2009.

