Tenderness/Pain at Wound Site (pain scale 0-10):

- A. None
- B. 1 to 2
- C. Greater than 3 to 4
- D. Greater than 4 to 7
- E. 8 to 10

Statistical Analysis Plan

Analyses: The primary outcome is wound closure by Week 12, which will be analyzed using Chi-square test to compare the percentages of subjects with complete closure in each group. We will also perform exploratory analysis with logistic regression, using the complete closure at 12 weeks as the dependent variable and the independent variables would include, treatment, size of ulcer, location on foot, how long ulcer has been present, previous revascularization (will analyze as subset group), offloading compliance, concomitant medications, foot deformity, history of amputation, diabetes complications index, CRP level, and glucose control (HbA1c). Selection of covariates will be performed by stepwise modeling procedures, and overseen by biostatistician [name].

Cost effectiveness analysis: We will perform a cost-effectiveness analysis comparing the treatment groups Dermagraft®, Apligraf®, Oasis® and the standard care group at the NCHCS using ANOVA or Kruskal-Wallis test depending if data is normally distributed for comparison of the three treatment arms. If significant, we will further analyze with pair-wise comparisons by using t-test or Wilcoxon rank-sum test with the Bonferroni correction to control for type I experiment-wise error rate of 0.05. A p-value less than $0.05/3 = 0.0167$ will be considered statistically significant.

We will evaluate the cost-effectiveness of the Oasis® compared to Dermagraft® or Apligraf® and the standard of care by measuring QALYs as the measure of effectiveness, based on results obtained from SF-36v2™ questionnaire. Multiple regression will be used to allow to evaluate continuous dependent variable outcomes, including change scores between baseline and end of study physical (PCS) and mental (MCS) component summaries from the SF36v2™ questionnaire.

Rates of healing among the four groups will be analyzed using log-rank test to compare time of healing within 20 weeks.

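### The cost-effectiveness analysis names one-variable tests without saying which variable they test, and no step joins cost to effect

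*Combined protocol and SAP*

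**What the plan says.** Cost-effectiveness is the secondary objective (Section 2) and a listed secondary efficacy outcome (Protocol Summary). The method appears in three places:

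- Protocol Summary, Data Analysis: secondary outcomes "will use ANOVA or Kruskal-Wallis test to analyze cost effectiveness".
- Section 6, Analyses: the three arms are compared "using ANOVA or Kruskal-Wallis test depending if data is normally distributed for comparison of the three treatment arms". If the result is significant, there follow "pair-wise comparisons by using t-test or Wilcoxon rank-sum test with the Bonferroni correction to control for type I experiment-wise error rate of 0.05", with a threshold of 0.05/3 = 0.0167.
- Appended Statistical Analysis Plan: the same tests and threshold, but with a fourth product in the list: "We will perform a cost-effectiveness analysis comparing the treatment groups Dermagraft®, Apligraf®, Oasis® and the standard care group".

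The next paragraph of Section 6 names QALYs, derived from SF-36v2, as the measure of effectiveness for Oasis against Dermagraft and standard care. The only model that follows is a multiple regression of change in the SF-36 component summaries. The Clinical Outcomes list in the same section assigns utilities and QALYs to EQ-5D instead.

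The only costs given are two device prices in Section 2: $1,800 per Dermagraft application and $80 per Oasis application. On course length, Section 4.2 says for each device "Up to 8 weekly applications will be applied to wound until healed". The Section 6 timeline says "Oasis® – continue to the end of study", and a note in Section 4.3.3 leaves room for a longer graft course.

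The documents do not define a test variable, cost items, cost perspective, time horizon, willingness-to-pay threshold, incremental ratio, net benefit or joint measure of uncertainty.

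**The concern.** Cost-effectiveness relates a difference in mean cost to a difference in mean effect. The planned tests compare one variable between arms and return a p-value. Without a variable that carries both cost and effect, they produce neither an incremental estimate nor its uncertainty.

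The choice of test adds a second problem. Cost data are usually skewed, so the normality rule would tend to select Kruskal-Wallis and Wilcoxon. Those tests compare ranks, whereas savings for the VA depend on mean cost per patient.

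What is at stake is whether the trial can say if the dearer product buys enough benefit to justify its price, and if either product does so against standard care. The primary closure comparison is not affected.

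**Working it through.** **1. The plan's own figure.** Three arms give three pairs, and 0.05/3 = 0.01667, printed as 0.0167. This reproduces. The SAP's list of four groups would give 4 × 3/2 = 6 pairs, so its list and its threshold do not match.

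**2. Device cost per treated subject.** Price (Section 2) × applications (1 to 8, Section 4.2):

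- Dermagraft: 1 × $1,800 = $1,800 to 8 × $1,800 = $14,400.
- Oasis: 1 × $80 = $80 to 8 × $80 = $640.
- Standard care: taken as $0, an assumption, since no dressing price is given.

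The ranges do not overlap: $1,800/$640 = 2.8.

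**3. Consequence for the tests if the variable is device cost.** Take 57 per arm and complete separation. The case least favourable to significance has no ties within a device arm.

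- Kruskal-Wallis: mean ranks are 29, 86 and 143. H = 12/(171 × 172) × 57 × (57² + 0 + 57²) = 151.1. The correction for 57 tied zeros is 1 − (57³ − 57)/(171³ − 171) = 0.963, so H = 156.9 on 2 df and p ≈ 8 × 10⁻³⁵.
- Wilcoxon, Dermagraft against Oasis: z = (57²/2 − 0.5)/√(57² × 115/12) = 1,624/176.5 = 9.20, p ≈ 3 × 10⁻²⁰.
- ANOVA and t-tests: a search over arms in which each subject has 1 or 8 applications found largest p-values of 4.5 × 10⁻¹² (ANOVA), 6 × 10⁻⁶ (t-test, Dermagraft against Oasis) and 2 × 10⁻⁸ (t-test, Oasis against standard care). These are the largest values found, not proven maxima.

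All lie far below 0.0167, whatever the healing results.

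**4. Sensitivity to course length and price.** Ranges stay apart while the price ratio exceeds the largest number of Oasis applications. The listed prices give 1,800/80 = 22.5. Twenty applications cost $1,600, still below $1,800; overlap begins at 23 ($1,840). If the end of study meant Week 28, 28 × $80 = $2,240 would overlap a one-application Dermagraft subject. Section 1 describes the price difference as 15-fold; at that ratio the ranges stay apart under the cap of 8 but not at 20.

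**5. What a test on cost leaves out.** Incremental device cost at equal courses is $1,720 for one application each and 8 × $1,720 = $13,760 for eight each. The documents give no threshold, so assume $50,000, $100,000 and $150,000 per QALY. The QALY gain needed to offset the extra cost is:

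| Applications each | $50,000 | $100,000 | $150,000 |
|---|---|---|---|
| 8 | 0.275 | 0.138 | 0.092 |
| 1 | 0.034 | 0.017 | 0.011 |

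The required gain varies about 24-fold (0.2752/0.0115). The cost p-value would be extreme in every cell.

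**6. If the variable is total cost.** The documents give no SD, so this is illustrative. With equal SDs, 57 per arm and two-sided 0.0167, an observed difference d is non-significant once SD exceeds d/(2.394 × √(2/57)) = d/0.448. For d = $6,880 (four applications each) that is about $15,300; for d = $13,760, about $30,700. On total cost the result is therefore not fixed in advance.

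**The case against.** **The tests could combine cost and effect.** A reader might infer that ANOVA is incapable of this. That is too strong: ANOVA on per-subject net monetary benefit would do it. But the plan defines neither that variable nor a threshold, so the gap remains.

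**The plan does name an effect measure.** It does: QALYs, with EQ-5D and SF-36v2 collected. It would be wrong to say that effect is ignored. Only the link to cost is missing, and the regression of component scores does not supply it.

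**Mean costs may be reported anyway.** Section 6 summarises continuous variables by mean and SD, and cost could be one of them. That would give arm means, but not a between-arm difference with a confidence interval.

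**Savings are stated as a consequence of equivalence.** If the two devices were shown to be equivalent, the savings question would reduce largely to a cost comparison. This has force for Oasis against Dermagraft, though a mean difference with its interval would still be needed rather than a rank test. It does not cover standard care, where the plan itself expects 25% closure against 50%.

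**Bootstrap intervals and acceptability curves are one accepted approach among several.** Agreed. The requirement is joint estimation, not a particular technique.

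**Conclusion.** The concern stands in this form: the tested variable is undefined, no step joins cost to effect, and the normality rule may replace a comparison of means with a comparison of ranks. Followed as written, the plan does not answer its secondary objective.

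A reader might go further and infer that the planned test is bound to be significant. The documents support that only if the variable is device cost alone, for subjects with at least one application, at the listed prices, and with no more than 22 Oasis applications. A few subjects who leave before a first application would have a device cost of $0 and break strict separation, without materially changing significance. No section restricts cost to devices, and total cost could overlap.

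Nor do the prices show which product is better value. That depends on applications used, other costs, QALYs and a threshold, none of which the documents fix.

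This is a secondary analysis that should be corrected; it leaves the primary result untouched.

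**What to change.** Replace the ANOVA/Kruskal-Wallis analysis and its normality-driven choice of test, in all three places, with the following:

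- Define the cost items, perspective and time horizon.
- Name one utility source (SF-36v2 or EQ-5D) and its assessment times. The Section 4.3 schematic puts the follow-up questionnaires at Visit 20, while Section 4.3.4 puts SF-36v2 at Visit 19.
- For each pair of arms, estimate the difference in mean cost, in mean QALYs and in the proportion of closed ulcers, with confidence intervals.
- Report incremental net monetary benefit (threshold × QALY difference − cost difference) over a stated range of thresholds, and the incremental ratio where it is meaningful. Adjust for baseline utility.
- Treat cost and effect jointly, for example with a bootstrap that resamples each subject's cost and QALYs together within arm. An acceptability curve is a useful addition.
- Bring the SAP's list of groups into line with the three arms, and the 15-fold statement into line with the listed prices.

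The passages on course length (Sections 4.2, 4.3.3 and the Section 6 timeline) must be reconciled, since device cost depends on them.

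The cost is SAP wording and modest extra analysis. A device-cost perspective needs no new data: it uses recorded applications, closure and the planned questionnaires. A wider VA cost perspective would need resource-use data, which the schedule does not list.

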7. Infected wounds or osteomyelitis (confirmed by bone biopsy, MRI or bone scan).
8. Active Charcot as described by Saunder's classification system.
9. Poor nutritional status, Albumin level < 2.9.
10. Ulceration size less than 1.0 cm² or greater than 20 cm².
11. Porcine allergy.
12. Chemistry tests serum creatinine, 2 times above the upper limits and LFTs 3 times above the upper limits.

TREATMENT: Total duration of study per subject: Up to 22 weeks (Includes to 2 weeks of screening and up to 12 weeks until the end of the follow-up period).

DURATION OF ADMININSTRATION: 8 weekly applications (starting at Visit 4/Week 1).

STUDY DESIGN: This is a randomized, single-blinded, four-armed controlled clinical equivalence trial comparing the effectiveness of three intervention arms (acellular ECM, Oasis® and a cellular ECM, fibroblast-only Dermagraft®) and a standard treatment arm.

EFFICACY ENDPOINTS:

PRIMARY EFFICACY OUTCOME

1. Complete closure of ulcer by Week 12

SECONDARY EFFICACY OUTCOME

1. Complete closure of ulcer by Week 20
2. Rate of ulcer healing

3. Cost effectiveness comparing Oasis® and Dermagraft®

QUALITY OF LIFE ASSESSMENT: We will also evaluate the cost-effectiveness of the Oasis® compared to Dermagraft® and the standard of care by measuring QALYs as the measure of effectiveness, based on results obtained from SF-36v2™ questionnaire. Multiple regression will be used to allow to evaluate continuous dependent variable outcomes, including change scores between baseline and end of study physical (PCS) and mental (MCS) component summaries from the SF-36v2TM questionnaire.

DATA ANALYSIS: The primary outcome is wound closure by Week 12, will use Chi-square test to compare the percentages of subjects with complete closure in each group. Exploratory analysis with logistic regression, using the complete closure at 12 weeks as the dependent variable and the independent variables would include, treatment, size of ulcer, location on foot, how long ulcer has been present, previous revascularization, offloading compliance, concomitant medications, foot deformity, history of amputation, diabetes complications index, CRP level, and glucose control (HbA1c). Selection of covariates will be performed by stepwise modeling procedures.

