4.3 STUDY FLOW CHART

Study Plan Schematic

Procedure	Visit 1 (Week -2)	Visit 2 (Week -1)	Visit 3 (Week 0) Randomization	Visits 4-10 (Week 1-7) Treatment	Visits 11-18 (Week 8-15) Treatment	Visit 19 (Week 16) Study Endpoint	Visits 20-23 (Week 17-28) Follow-Up
Informed Consent	X						
Inclusion/Exclusion Criteria	X	X	X				
Physical Exam	X					X	
Vital Signs	X	X	X	X	X	X	
Ankle-Brachial Index	X						
Fungal Infection Culture and Malignancy Evaluation	X						
Blood Sample Drawn for Labs	X						
SF-36v2™, EQ-5D, QALYs Questionnaires	X						Visit 20 only
Ulcer Assessment	X	X	X	X	X	X	X
Debridement	X	X	X	X	X	X	X
Ulcer Photography and Area Measurement	X	X	X	X	X	X	X
Randomization			X				
Dermagraft® Tx + SOC			X	X			
Oasis® Tx + SOC			X	X			
SOC	X	X	X	X	X	X	X
Concomitant Medications	X	X	X	X	X	X	X
Adverse Events	X	X	X	X	X	X	X

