4.3.4 Study Endpoint (Visit 19/Week 16)

- Subjects to complete the health-related quality of life survey, the Medical Outcomes Study 36 item Short Form (SF-36v2™) health survey.
- Vital signs will be obtained and recorded.
- The ulcer will be assessed – visual inspection – complete ulcer characteristics form (see appendix). Determine if reaches 100% epithelization determined by clinician.
- Labs drawn from each subject, hematological and chemistry panel. Pregnancy test of childbearing age.
- If concern for infection, confirmatory bacterial culture will be obtained (deep swab culturette or tissue specimen/biopsy). Radiographical x-rays and blood work (CBC, ESR, CRP, and Chem) may also be performed if deemed necessary by investigator clinician.
- Digital imaging of ulcer location, if remains non-healing then 2 images to be obtained prior to and after surgical debridement.
- Surgical debridement of ulcer if not healed, will be performed using curette or blade and standard therapy.
- Changes in concomitant medications, adverse events, compliance to offloading, will be recorded.

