- Number of incident subjects with infection, osteomyelitis and acute Charcot during the study, will be withdrawn from the study.
- Number of incidence of adverse effects will be reported from all sites, and will be withdrawn from the study.
- Veterans' Short Form Health Survey (SF-36v2TM), a self-administered questionnaire will be used to measure quality of life, given at beginning and at the end of the study.
- EuroQol Questionnaire (EQ-5D) to evaluate overall quality of life and to facilitate the calculation of health utilities and quality adjusted life years (QALYs). The EuroQol questionnaire (EQ-5D) will be administered at beginning and at the end of the study.

Sample Size Estimation:

The sample size was estimated based on 80 percent power, significance level 0.05, to detect a difference in the incidence of ulcer closure of the two study groups and the standard of care group (Stplan4.3).⁴ It is expected that 50% of the Dermagraft® and Oasis® groups will reach complete ulcer closure by Week 12 and approximately 25% closure with those subjects that received the standard of care (numbers based on previous studies as described previously). We would expect the difference to be 25% between the standard and the treatment group. By using a Chi-square test without continuity correction test would require 57 subjects in each group. If we estimate the difference to be 20% and lower of the cure rates to be 30%, then we would require 88 patients in each group.

Analyses:

The primary end point is wound closure by Week 12, which will be analyzed using Chi-square test to compare the percentages of subjects with complete closure in each group. We will also perform exploratory analysis with logistic regression, using the complete closure at 12 weeks as the dependent variable and the independent variables would include, treatment, size of ulcer, location on foot, how long ulcer has been present, previous revascularization (will analyze as subset group), offloading compliance, concomitant medications, foot deformity, history of amputation, diabetes complications index, and glucose control (HbA1c). Selection of covariates will be performed by stepwise modeling procedures.

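### The plan assigns the QALY calculation to two different questionnaires, states a utility scoring for neither, and schedules the final questionnaire at two different visits

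*Combined protocol and SAP*

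**What the plan says.** Section 2 makes cost-effectiveness of the cellular against the acellular product the secondary objective.

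**Source of the QALYs.** Section 6, Analyses, evaluates cost-effectiveness by "measuring QALYs as the measure of effectiveness, based on results obtained from SF-36v2™ questionnaire". The Protocol Summary (Quality of Life Assessment) and the SAP's cost-effectiveness paragraph use the same phrase. The only SF-36v2 scores named in these texts are the physical and mental component summaries (PCS and MCS), whose change scores go into a multiple regression.

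The outcome list in Section 6 (Clinical Outcomes) divides the work differently. SF-36v2 is "a self-administered questionnaire will be used to measure quality of life, given at beginning and at the end of the study". EQ-5D is collected to evaluate overall quality of life and "to facilitate the calculation of health utilities and quality adjusted life years (QALYs").

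**Timing.** The same list says "The EuroQol questionnaire (EQ-5D) will be administered at beginning and at the end of the study". The flow chart in Section 4.3 has one row, "SF-36v2™, EQ-5D, QALYs Questionnaires", marked at Visit 1 and at Visit 20 only; the table of contents places Visit 20 at Week 17. The visit texts differ from this. Section 4.3.1 (screening) lists SF-36v2 alone. Section 4.3.4 (Visit 19/Week 16) says "Subjects to complete the health-related quality of life survey, the Medical Outcomes Study 36 item Short Form (SF-36v2™) health survey" and does not mention EQ-5D. Section 4.3.5, which covers Visit 20, lists no questionnaire.

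**The concern.** A QALY is a utility multiplied by time. To compute one, the plan must fix which questionnaire supplies the utility, how its answers are scored as a utility, and over what period. Here the first is stated in two incompatible ways, the second is not stated, and the third follows a schedule that differs between the flow chart and the visit texts.

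The stake is the secondary objective, on which the proposed savings depend. Section 1 expects equivalent clinical outcomes, so the QALY difference between the two products is expected to be small. Where the expected difference is small, the choice of instrument and period can matter to how the comparison reads. As written, the questionnaire collected for QALYs has no analysis, and the questionnaire named in the analysis has no route to a utility.

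**Working it through.** **The plan's own figure.** The only number attached to the cost-effectiveness comparison is the pairwise threshold: 0.05 / 3 = 0.01667, which rounds to the stated 0.0167. It reproduces and is not in question.

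**The texts side by side.**

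| Place | SF-36v2 | EQ-5D | When |
|---|---|---|---|
| Protocol Summary | QALY source; PCS and MCS regression | not mentioned | baseline and study end |
| 4.3 flow chart | same row as EQ-5D and QALYs | same row | Visit 1; Visit 20 (Week 17) |
| 4.3.1 | listed | not listed | screening |
| 4.3.4 | listed | not listed | Visit 19 (Week 16) |
| 4.3.5 | not listed | not listed | Visits 20 to 23 |
| 6, Clinical Outcomes | quality of life | utilities and QALYs | start and end of study |
| 6, Analyses | QALY source; PCS and MCS regression | not mentioned | baseline and study end |
| SAP | QALY source; PCS and MCS regression | not mentioned | baseline and study end |

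**Can they be reconciled?** There are three possible readings.

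1. SF-36v2 is the source and EQ-5D is supportive. This fits the three analysis texts but contradicts the purpose that Section 6 gives EQ-5D.
2. EQ-5D is the source. This fits the outcome list but contradicts all three analysis texts.
3. Both are used. No text ranks them, combines them or calls one a sensitivity analysis.

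The flow chart row groups both instruments with QALYs and so does not decide between them.

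**Is the named source usable as written?** PCS and MCS are health-status summaries, not utilities, and the plan uses them in a separate regression. A utility can be derived from SF-36, but no text says which derivation applies. No EQ-5D scoring or value set is named either.

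**Timing.** Counted from randomisation (Week 0), the final questionnaire falls at 16 weeks (Section 4.3.4) or 17 weeks (flow chart): 17 / 16 = 1.0625. Counted from the Visit 1 questionnaire at Week -2, it is 18 or 19 weeks: 19 / 18 = 1.056.

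As an illustration, assume equal utilities at randomisation and a linear divergence to a between-arm difference d at the final questionnaire. Then

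QALY difference = 0.5 × d × weeks / 52.

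- Week 16: 0.5 × 16 / 52 = 0.154 × d
- Week 17: 0.5 × 17 / 52 = 0.163 × d

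For the same d, the visit conflict alone moves the QALY difference by about 6%. The phrase about the end of the study in Section 6 does not settle the visit: the plan labels Week 16 the study endpoint, takes its final secondary measurement at Week 20, and has its last follow-up visit at Week 28.

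**The case against.** The strongest reply is that the analysis source is not in doubt. Three analysis texts, the SAP among them, name SF-36v2 and none names EQ-5D; the outcome list says only that EQ-5D helps with the calculation. The PCS and MCS scores belong to a separate regression, so the plan never claims that QALYs come from them, and a utility can be derived from SF-36. The flow chart lists EQ-5D at both time points, so it does not follow that sites would omit it. Only a secondary objective is touched.

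Much of this stands. A strict reader of the analysis texts would use SF-36v2, and that could be made to work. But the reply leaves the conflict inside Section 6, where a questionnaire collected expressly for QALYs has no analysis, and it does not supply the missing scoring. Nor does it resolve the two final visits.

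Three stronger readings are tempting, and the documents do not support them.

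- A reader might infer that the instrument could be picked once the results are known. No text says so, and the analysis texts are consistent in naming SF-36v2. Any figure for an inflated error rate would need a correlation between instruments that the documents do not give.
- A reader might turn the conflict into two costs per QALY. The plan names no such ratio; it specifies ANOVA or Kruskal-Wallis with pairwise tests. The documents give prices of $1,800 and $80 per application, but applications run up to 8 until healing, so the cost difference per patient is not fixed, and utility gains would have to be invented.
- A reader might take Week 20 as the QALY horizon. Section 2 does place secondary outcomes at 20 weeks, but the analyses tie that week to closure, recurrence and time to healing. No QALY horizon is stated.

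**Conclusion.** The point holds as a contradiction in current text about a stated secondary objective. Section 6 collects EQ-5D for QALYs and then bases QALYs on SF-36v2; no utility scoring is given; and the final questionnaire is at Week 16 with SF-36v2 alone in one place and at Week 17 with both instruments in another. These are conflicting instructions, not merely missing detail.

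Its size can be given only in part. The effect of the instrument cannot be calculated, because the documents contain no utility values. The visit conflict is one week, about 6% of the QALY difference under the linear assumption above. The primary Week 12 closure analysis does not depend on either questionnaire and is unaffected. This should be corrected, and it can be corrected before the analysis.

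**What to change.** Before any analysis by treatment arm:

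1. Name one instrument and its utility scoring (algorithm or value set) as the QALY source, in the same words in the Protocol Summary, Section 6 Clinical Outcomes, Section 6 Analyses and the SAP. EQ-5D is the natural choice because Section 6 already collects it for this purpose. SF-36v2 would also be coherent if its utility derivation were stated and the EQ-5D entry amended.
2. Label a utility from the other instrument as a sensitivity analysis. Keep the PCS and MCS regression as a separate quality-of-life analysis.
3. Adjust the QALY comparison for baseline utility, which the Visit 1 questionnaire already provides.
4. List both questionnaires in the visit texts. Set one final questionnaire visit, an existing one, and make it identical in the flow chart, the visit texts and the Section 6 outcome list. State the QALY horizon to match.

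If questionnaires have already been completed, item 4 can only document what was collected and when. The choice in item 1 should then take completeness into account, judged without reference to arm.

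The cost is minor wording, one baseline covariate in the QALY comparison and a small sensitivity analysis. No new visit or instrument is needed.
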